Appendix 1.4 User Manual- to be sent home with subjects

Appendix 1.4 User Manual- to be sent home with subjects

## Appendix 2.1: Letter to oncologists requesting patient referrals

Dear Dr. \_\_\_\_\_,

I am writing to share details about an upcoming study being conducted by Partners Healthcare Connected Health Innovation, a research division of Massachusetts General Hospital, in collaboration with the MGH Cancer Center and the Dana Farber Cancer Institute's Pediatric Oncology department. [name], MPH is the PI on this project. The primary aim of this study (DFCI Protocol 14-485) is to assess the feasibility of the iThermonitor device as a clinical support tool in the management of pediatric patients undergoing myelosuppressive therapies. The iThermonitor is an electronic device that continuously measures the wearer's body temperature. It is secured to the skin via hydrogel dressing. Full technical details of the device and its functionality are included below.

A total of 25 dyads will be enrolled in this study. Dyads will include one pediatric cancer patient and his/her caregiver. The caregiver will be asked to use the iThermonitor device for a period of 2 weeks to monitor the child's body temperature. Upon registering and creating an account on the iThermonitor mobile application, the device will be paired with a wirelessly enabled iPad Mini or Smartphone receiver which should be within 3 meters of each other. Upper and lower temperature limits can be set on the device to alert users when temperatures are outside of pre-set range. However, for this study, the range will be fixed at less than or equal to 96 and greater than or equal to 100 as recommended by the pediatric oncology team at MGH. If you would like to review a more detailed description of the protocol, please let me know and I'll be happy to share that with you.

There will be 2 study visits (enrollment and closeout) and patient/caregiver dyads will receive a total of \$100 for their participation. The eligibility criteria are as follows:

- Pediatric patient Aged 2- 17 years
- English speaking patient/caregiver (18 yrs or older)
- Undergoing myelosuppressive therapies for acute leukemia or other childhood cancers.
- If applicable, willingness of the patient to shave axillary (armpit) hair.

We are excluding patients who may have:

## Appendix 3.1: Parent phone script

**Screener's Name** \_\_\_\_\_

**Date:** \_\_\_\_\_

**Are you interested in participating in the study?**

[If No]: Okay, thank you for your time.

[If Yes]: Great, when would you be available to meet?

Do you have any final questions? [Answer questions]

Thank you for taking the time to speak with me and for your interest in this study. I look forward to meeting with you on [Date, time, location]. Have a nice day.

Appendix 3.2: Appointment reminder letter to parents

[Date]

Dear \_\_\_\_\_,

Thank you for your participation in the iThermonitor study. This is a friendly reminder that your final study visit is scheduled for the following time:

Date: \_\_\_\_\_

Time: \_\_\_\_\_

Location: \_\_\_\_\_

Take along: **smartphone/provided iPad Mini**

At this study visit, we'll ask you to complete some surveys about your experience using the iThermonitor device. You will receive a \$100 check for completing the study. If you have been using a study-provided iPod Touch, you will only receive this check upon returning the iPod Touch.

Please feel free to contact us with any questions or concerns at [###-###-####]. We look forward to seeing you!

Best Regards

\_\_\_\_\_

Study Staff  
iThermonitor Study

**1. The following are statements about your experience using the iThermonitor. Please rate how much the following statements concerning the iThermonitor are true for you. (Please circle the number of your answer):**

	Definitely NOT true	A little bit true	Mostly true	Definitely true
1) Overall, I am satisfied with how easy it was to use the device	1	2	3	4
2) It was easy learning to use the device	1	2	3	4
3) I felt comfortable using the device	1	2	3	4
4) I was able to easily monitor my child’s temperature by using this device	1	2	3	4
5) I feel more confident monitoring my child’s temperature by using the device	1	2	3	4
6) The device was helpful in starting discussions about my child’s health with my doctor	1	2	3	4
7) Using the device makes me feel more connected to my care team	1	2	3	4
8) I found the mobile application very useful in monitoring my child’s temperature	1	2	3	4
9) I found the out-of-range temperature alert function very useful when my child’s temperature was out of range	1	2	3	4
10) I would recommend iThermonitor to a friend or family member	1	2	3	4
11) The iThermonitor stayed on my child’s body for most days during the study.	Yes		No	

---

12) I was able to view my child's temperature data on the provided iPad mini for most days during the study.	Yes	No
--	-----	----

---

**2. Did you view your child's temperature on the iThermonitor app?**

(Please circle one of these options)

- a. Yes
- b. No
- c. Prefer not to answer

**3. Did you use another device other than the provided iPad mini to monitor your child's temperature? (Please circle one of these options)**

- a. Yes
- b. No
- c. Prefer not to answer

**4. How often did you view the measurements? (Please circle one of these options)**

- a. Hourly
- b. 2-hourly
- c. 4-hourly
- d. Daily
- e. 2-3 times per week
- f. Once a week
- g. never
- h. other: \_\_\_\_\_

**5. Was viewing measurements on the app useful in being able to better manage your child's health? (Please circle one of these options)**

- a. Yes
- b. No
- c. Prefer not to answer

**6. Did viewing measurements on the app help you become more interested in your child's health? (Please circle one of these options)**

- a. Yes
- b. No
- c. Prefer not to answer

**7. Did you discuss the iThermonitor device with others?**

*(Please circle **one** of these options)*

- a. Yes
- b. No
- c. Prefer not to answer

**8. Did you discuss the iThermonitor device with your doctor?**

*(Please circle **one** of these options)*

- a. Yes
- b. No
- c. Prefer not to answer

**9. If you were given the choice would you like to continue using the iThermonitor device to monitor your child's health?**

*(Please circle **one** of these options)*

- a. Yes
- b. No
- c. Prefer not to answer

**10. If the iThermonitor were for sale in a store, would you buy it?**

*(Please circle all that apply)*

- a. Yes, for my child.
- b. No
- c. Prefer not to answer
- d. Yes, for someone else (please tell us who): \_\_\_\_\_

**11. How much do you like the components of the iThermonitor system below?**  
(Please circle the number of your answer)

	Not at all	A little bit	I like it	Very much
a) Continuous temperature monitoring	0	1	2	3
b) Viewing measurements on the app	0	1	2	3
c) Alerts when measurements are out of range	0	1	2	3
d) Other (please specify): _____ _____	0	1	2	3

**12. Did you experience problems using the iThermonitor?**  
(Please circle **one** of these options)

- a. Yes
- b. No\*
- c. Prefer not to answer \*

*\*[If No or "Prefer not to answer", skip to question 14]*

**13. What problems did you experience?**  
(Please circle **all that apply**)

- a. Problems keeping the device on my child's body
- b. Problems linking the device with my smartphones
- c. Problems with the iThermonitor battery
- d. Problems setting out-of-range temperature alerts
- e. Other problems: \_\_\_\_\_

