### 6.1 Primary and secondary endpoints

6.1a Primary outcome measurement: use feasibility of the iThermonitor will be assessed by ability of the device to successfully capture, transmit and display the patient's body temperature data on the study iPad mini. To limit recall bias, subjects will be required to log (Appendix 5) the ability to view the temperature data on the iPad mini once a day for the entire duration of the study. The device will be deemed a feasible continuous temperature monitoring tool if at least 80% of study subjects are able to successfully use the iThermonitor to monitor their body temperature. A subject must be able to view temperature data on the provided iPad mini at least 80% of the time in the study to be considered successful. "Time in the study" here is defined as the number of days the subject spends in the study which is expected to be two weeks.

6.1b Secondary outcomes: secondary outcomes which will be assessed at the end of the study include:

- i. Usability, acceptability and satisfaction with the iThermonitor. This will be assessed by questionnaires specifically designed for this study. We will be assessing ease of use, acceptability, connection and use problems like the device falling off the skin, usefulness of out-of-range temperature alerts and adverse reactions. We will also assess to see if the device helps to build caregiver self-efficacy skills in caring for the patient.
- ii. Caregiver engagement with the iThermonitor. This will be assessed by time to first measurement and upload from the time of discharge and also by the frequency of logins to the iThermonitor app.
- iii. Caregiver anxiety will be assessed using the GAD-7 questionnaire.

6.2 Sample size and statistical power or precision associated with the sample size: The length of time required to accrue an adequate number of subjects to the study should be indicated.

We will be able to estimate a feasibility success rate of 80% to within a 95% confidence interval of +/- 16% with a sample size of 25 evaluable patients. This is in keeping with a

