## Using and maintaining the iThermonitor

- Charge the iPad regularly and keep the iThermonitor app open. Do not log out of the app.
- Make sure the Bluetooth is in the on position.
  - If you have a Wi-Fi connection in your home, connect the iPad to the Wi-Fi to allow the iThermonitor to sync for data collection.
- DO NOT change settings of the iPad or the iThermonitor app.
- DO NOT get the iThermonitor wet (shower, bath swimming, etc).
- DO NOT wear the iThermonitor at one side for more than 24 consecutive hours. Change sides everyday to wear it for continuous monitoring.
- If your child feels unwell (uncomfortable or allergic) when using the patch, replace it with another type of adhesive dressing based on your doctor's advice. A fully-covered patch larger than 76mm×62mm should be used.
- Do not reuse the patches. If a patch is already folded over, a new patch is required.

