**14. Please explain in detail the nature of the problem(s) you experienced as marked above:**

---

---

---

---

---

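### The close-out problem list (Appendix 4.1, Q13) names neither the study iPad mini nor a missed alert, so neither problem can be tabulated reliably; Q3 does not cleanly identify use of an own phone or tablet

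*Combined protocol and SAP*

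**What the plan says.** Section 6.1b(i) lists what the study questionnaires will assess, including "connection and use problems like the device falling off the skin, usefulness of out-of-range temperature alerts and adverse reactions". Section 2.21 places the ability of the device to alert the caregiver under the primary aim. Section 5.3 describes the iPad mini as the receiver, and section 6.1a defines success by viewing data on it.

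Appendix 4.1, Q13, lets the caregiver mark any number of problems from five options:

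- a: keeping the device on the child
- b: "Problems linking the device with my smartphones"
- c: the battery
- d: "Problems setting out-of-range temperature alerts"
- e: "Other problems", with a blank line

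Q14 follows with "Please explain in detail the nature of the problem(s) you experienced as marked above".

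Section 5.3 fixes the alert limits for every participant, and the user guide in Appendix 1.4 says "DO NOT change settings of the iPad or the iThermonitor app".

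Q3 of the same survey begins "Did you use another device other than the provided iPad mini" and goes on to refer to monitoring the child's temperature. It does not say what kind of device is meant.

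**The concern.** Option b names a receiver that most of the protocol treats as an optional addition, and leaves out the one on which success is defined. Option d names a task that caregivers are told not to do, and leaves out the alert failure that the protocol itself identifies: section 5.5 gives failure to notify the caregiver of a true fever episode as one of the main risks. Q3 is the only survey item that asks directly about a receiver other than the iPad mini, and its wording also fits an ordinary thermometer.

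At stake is whether the survey can deliver two things that the protocol says it will assess: connection problems, in a form that shows which receiver was involved, and the working of the alerts. A feasibility pilot is more useful to the next study if it can say why the data did not reach the screen. That information may not be recoverable once close-out is complete.

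**Working it through.** **The plan's own figure.** The plan states no rate or precision for connection or alert problems. Its only precision figure is ±16% for an 80% success rate with 25 evaluable patients (section 6.2). It reproduces: 1.96 × √(0.8 × 0.2 / 25) = 0.157. It concerns the primary endpoint and does not bear on this point. The check is therefore mainly a comparison of texts.

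**Connection problems.** The outcome promised is "connection and use problems like the device falling off the skin". A caregiver whose iPad mini would not link has three routes in Q13: write it under option e, mark option b as the nearest match, or mark nothing. The first depends on the caregiver's effort and on later coding. The second counts a connection problem but merges it with own-phone problems. The third loses it. Q14 asks only about problems already marked.

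**What the other items record:**

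| Item | What it shows | What it leaves open |
|---|---|---|
| Daily log, viewing column | Whether data could be viewed on the iPad mini, each of 14 days | Cause of a No: link, battery, device off the body, iPad not charged, another receiver used |
| Daily log, wear column | Whether the device stayed on for most of the day | Separates only wear from the other causes |
| Q1 item 12 | Viewing on the iPad mini on most days | Cause, as above |
| Q1 item 9 | Rated usefulness of the alert | Whether any alert failed |
| Q16 | Whether the device alerted when temperature was out of range | A No can mean no out-of-range episode or no alert |
| Q17 | How often the device detected out-of-range temperatures | Whether each detection reached the caregiver |

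The uploaded temperature record need not show a lost link either. The sensor stores up to 10 days of readings and transfers them when the connection returns (section 5.3 and Appendix 1.4).

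**Alerts.** The limits are fixed and the app settings are not to be changed, so option d asks about something caregivers should not have attempted. No option covers an alert that did not arrive or went unnoticed, and the daily log has no alert column.

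**Q3.** Section 5.3 tells caregivers to confirm alerts with their usual method or own thermometer, and section 5.5 tells them to continue monitoring as their care providers recommend. A caregiver who did so could truthfully answer Yes to Q3. Section 5.3 also lets a caregiver who prefers their own device have the app installed on it, which can be read as use in place of the iPad mini. A Yes does not show which of these happened.

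**Size.** One dyad in 25 is 1/25 = 4 percentage points. Going further needs two rates that the documents do not give: the true proportion of dyads with an iPad mini link problem, and the share of those identifiable as such from Q13. Expected dyads shown = 25 × true proportion × share identified. Both rates below are assumptions, for illustration only.

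| Assumed true proportion | Share identified | Expected dyads shown | Shown in Q13 |
|---|---|---|---|
| 20% (5 dyads) | 25% | 1.25 | 5% |
| 20% (5 dyads) | 100% | 5 | 20% |
| 40% (10 dyads) | 25% | 2.5 | 10% |
| 40% (10 dyads) | 100% | 10 | 40% |

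With everything identified there is no loss. The result runs from no effect to a large one, depending entirely on a rate that nobody knows.

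**The case against.** The survey is not closed to these problems. Option e and Q14 accept free text, and Q18 offers a conversation with staff. Section 5.65 has research assistants administer the questionnaires, so wording can be clarified, though the online REDCap close-out weakens that. Staff telephone if no data arrive by the second day (section 5.63). Own devices are a genuine study connection under section 5.3, so option b is not misplaced; it is incomplete. Q3 directly follows a question about the app, so many caregivers will take it to mean another receiver. The outcomes are descriptive (section 6.7), and no analysis linking Q13 to failure on the primary endpoint is planned.

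The ambiguity of Q16 can also be narrowed. Section 5.4 lists the number of out-of-range episodes detected, so a No could be set against the device record. The plan does not say that this will be done, and a single answer for the whole period would still hide one missed alert among several received.

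All of this limits the consequence. It does not supply a fixed option for either problem, and free text from about 25 caregivers is a weak basis for a count.

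A reader might infer more than this: that reported connection problems will be biased downward, that the primary result is compromised, or that nearly every caregiver will answer Yes to Q3. The documents do not support these readings. An iPad mini problem marked under option b is misclassified by receiver but still counted as a connection problem. The primary endpoint comes from the daily log, not from Q13. The ambiguity in Q3 does not cause connection problems to be missed, and nothing shows how caregivers would read it.

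**Conclusion.** The point holds as a minor fault of the instrument. The fixed list in Q13 does not name the study receiver or a missed alert, so the form as written cannot reliably tabulate connection problems by receiver or separate out alerts not received. Q3 is a separate ambiguity: it does not cleanly identify use of an own phone or tablet.

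The size of any under-count or misclassification cannot be computed. It could be nil if caregivers write these problems in fully and the text is coded. The conclusion rests on the wording of the items alone and assumes that the REDCap form matches the paper one. The primary endpoint calculation, sample size and decision rule are unaffected.

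**What to change.** Reword three items in Appendix 4.1, on paper and in REDCap:

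- **Q13b:** split into *Problems connecting to the provided iPad mini* and *Problems connecting to my own phone or tablet*.
- **Q13d:** replace with *Out-of-range alerts not received or not noticed*.
- **Q3:** *Did you use a phone or tablet other than the provided iPad mini to view the iThermonitor readings?*

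The new Q13d will capture only missed alerts that the caregiver came to know of, for example from a thermometer reading or from viewing the data later, and should be reported with that limit.

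The cost is an edit to three survey items and the usual approval of a revised questionnaire. Nothing changes in design, sample size, analysis or clinical management. If some dyads have already completed the existing form, report their answers separately, with the free text from Q13e and Q14 coded by receiver where it allows.

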**14. Please explain in detail the nature of the problem(s) you experienced as marked above:**

---

---

---

---

---

**15. What else would you want added to the iThermonitor system to help to you better monitor your child's health?**

---

---

---

---

---

**16. Did the iThermonitor alert you when your child's temperature was of out-of-range during the study period?**

- a) Yes
- b) No
- c) Prefer not to answer

*\*[If No or "Prefer not to answer", skip to question 17]*

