**17. How many times did the iThermonitor detect out-of-range temperatures? (If multiple times, please indicate number)**

- a) Once
- b) Twice
- c) 3 times
- d) Other: \_\_\_\_\_times

**18. We understand that this questionnaire may not fully capture your experiences participating in this study. Would you be interested in speaking with a research staff about your experiences in this research study?**

- a) Yes
- b) No

**Your answers are important to us. Please take a moment to check that you have answered all of the questions. Thank you for taking the time to complete this questionnaire!**

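### Close-out survey: the Q16 and Q12 skips are off by one, alert usefulness has no 'not applicable', and a Q16 'No' does not separate 'no episode' from 'no alert'

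*Combined protocol and SAP*

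**What the plan says.** The relevant text is in the close-out survey (Appendix 4.1) and in sections 2.21, 5.3 to 5.5, 6.1b, 6.7 and 6.8.

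- **Q16** asks "Did the iThermonitor alert you when your child's temperature was of out-of-range during the study period". Those who answer 'No' or 'Prefer not to answer' are told to "skip to question 17".
- **Q17** asks "How many times did the iThermonitor detect out-of-range temperatures". The options are once, twice, three times, or 'Other' with a blank for a number. Q18, the last question, is about interest in speaking with research staff.
- **Q12** asks about problems using the device. 'No' and 'Prefer not to answer' lead to the instruction "skip to question 14". Q14 reads "Please explain in detail the nature of the problem(s) you experienced as marked above".
- **Q1 item 9** begins "I found the out-of-range temperature alert function very useful when my" and refers to the time when the child was out of range. It is scored from 1 (definitely not true) to 4 (definitely true), with no other option.
- **Section 6.1b, item i** names "usefulness of out-of-range temperature alerts" as part of the first secondary outcome, measured by questionnaire.
- **Section 2.21** adds that the device's ability to alert the caregiver will be assessed.
- **Section 5.4** lists the number of out-of-range episodes in its own row, marked for the study period. The close-out surveys are a different row.
- **Sections 6.7 and 6.8** give descriptive summaries for these items, on complete cases.

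**The concern.** A skip that leads to the next question does nothing. At Q16, a caregiver who has just reported no alert is asked how often the device detected an out-of-range temperature. At Q12, a caregiver who reported no problems is asked to explain the problems.

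Item 9 matters more, because it feeds a named secondary outcome. It asks for a rating of something that, for some caregivers, did not happen. The plan has no rule restricting its summary to those who had an alert, so the reported figure could combine experience of alerts with guesses about them.

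The wording of Q16 raises a separate problem. 'No' is the correct answer both for a child who was never out of range and for a child who was out of range without an alert being received. The first says nothing against the device. The second is the failure that section 2.21 sets out to look for and that section 5.5 names as a study risk. It could plausibly occur: under section 5.3 the sensor keeps recording without a receiver connection, whereas the alert appears on the receiver.

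**Working it through.** **Tracing the routing**

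| Item | Answer | Printed target | What the target asks | First item that does not presuppose the event |
|---|---|---|---|---|
| Q16 | No / Prefer not to answer | Q17 | Count of out-of-range detections | Q18 |
| Q12 | No / Prefer not to answer | Q14 | Detail of the problems marked | Q15 |

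Both targets fall one item short. The Q12 skip at least passes Q13; the Q16 skip passes nothing.

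**The plan's own figure.** The only design figure is in section 6.2: ±16% around 80% with 25 evaluable patients. It reproduces: 1.96 × √(0.8 × 0.2 / 25) = 0.157. It concerns the primary endpoint and does not depend on the survey.

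**Item 9: possible range of the reported mean.** The documents do not say how many caregivers will have no alert. Assume k = 5, 10 or 15 of 25, a mean of 3.0 among those who had one, and that all of the k caregivers answer the item.

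- Lowest mean (all k score 1): [3.0 × (25 − k) + 1 × k] / 25
- Highest mean (all k score 4): [3.0 × (25 − k) + 4 × k] / 25

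| k | Lowest | Highest | If all k leave it blank |
|---|---|---|---|
| 5 | (60 + 5)/25 = 2.60 | (60 + 20)/25 = 3.20 | 3.0 |
| 10 | (45 + 10)/25 = 2.20 | (45 + 40)/25 = 3.40 | 3.0 |
| 15 | (30 + 15)/25 = 1.80 | (30 + 60)/25 = 3.60 | 3.0 |

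These are bounds, not predictions. The distortion can go either way or be nil.

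**Q17: the recalled count.** Assume also a mean of 2 episodes among caregivers with an alert and a true 0 among the others.

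| k | True mean, 2 × (25 − k)/25 | All k tick 'once', [2 × (25 − k) + k]/25 | All k leave it blank and are dropped | All k write 0 |
|---|---|---|---|---|
| 5 | 1.6 | 1.8 | 2.0 | 1.6 |
| 10 | 1.2 | 1.6 | 2.0 | 1.2 |
| 15 | 0.8 | 1.4 | 2.0 | 0.8 |

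Under these response patterns the error in the recalled count is upward or zero.

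**Q16: is the missing distinction available elsewhere?** The daily log (Appendix 5.2), as shown, has two columns: whether the device stayed on and whether the data could be viewed. Neither records an alert, although section 5.3 asks caregivers to log false alarms. The device record (section 5.4) holds temperatures but is not described as holding alerts received. In the available text, Q16 is the only item that directly asks whether an alert reached the caregiver. Setting its answer against the device record and the fixed alert limits would separate no recorded excursion from a recorded excursion with no reported alert. The data for this are collected, but the plan does not state the comparison.

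**The case against.** The case for leaving the form alone has real substance, and it limits the point in several ways.

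- A reader might infer that a caregiver with no alert cannot answer Q17. That is not so: the 'Other' line accepts 0. What is missing is a printed zero.
- A reader might infer that item 9 forces a score. Section 5.5 lets participants leave any question blank, and section 5.65 has research assistants administer the questionnaires, so an inapplicable item can be explained. Against this, the form ends by asking caregivers to check that every question is answered, and close-out may be done online. The REDCap build is not shown, so its routing is unknown.
- A reader might infer that the study's episode count is corrupted. The documents do not support this. The count is not a 6.1b outcome, section 5.4 places it during the study, and nothing names Q17 as its source. How the count is derived is not stated either.
- A reader might infer that usefulness must look worse as fewer children go out of range. That requires caregivers without an alert to score low, which is an assumption.
- Analysis can repair part of this. Item 9 can be tabulated among those answering 'Yes' at Q16, and a 'No' at Q16 followed by a positive count at Q17 is visible and can be set aside. Q11c also asks how much caregivers like the alerts.
- Q14 is free text, so the Q12 slip affects no outcome.

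All of this stands. What remains is that the plan states none of these repairs, and that Q16 alone cannot identify a missed alert.

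**Conclusion.** The point holds, and it is minor. Two skip targets are wrong on the face of the form. Item 9 has no 'not applicable', and no summary rule keeps caregivers without an alert out of a named component of secondary outcome i. Q16 'No' merges two different results, which weakens the alert assessment in section 2.21 unless Q16 is linked to the device record; the plan does not state that link.

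The documents support saying that the item 9 summary could be distorted, not that it will be. The ranges above rest on an assumed number of caregivers without an alert and assumed scores. The primary endpoint, its confidence interval, the sample size and the section 5.4 episode count are not shown to be affected.

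**What to change.** In Appendix 4.1 and its REDCap version:

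1. Send 'No' and 'Prefer not to answer' at Q16 to Q18, and at Q12 to Q15.
2. Split 'No' at Q16 into two answers: never out of range as far as the caregiver knows, and out of range but no alert came.
3. Add a 'not applicable, no alert occurred' option to Q1 item 9.

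In section 6.7:

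4. State that item 9 is summarised only among caregivers who report an alert, with that number given.
5. State that the Q16 answer will be compared with the device record against the fixed alert limits.

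A printed zero at Q17 is optional once the Q16 skip is corrected.

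The cost is a few edits to one form and two sentences in the analysis plan. Item 9 will rest on fewer dyads: 20, 15 or 10 instead of 25 in the illustration. That loses some precision, but every rating then comes from a caregiver who reports an alert. The split at Q16 should be made before surveys are collected, because the form alone cannot recover it afterwards.
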